5.3 Governing Body Review

All dialysis facilities have a CMS mandated governing body responsible for facility-level operations. The governing body typically includes the medical director (nephrologist), facility manager, and members of the nursing or social work teams. This governing body meets monthly to review facility data. Among the selected facilities, we will review study goals and procedures for the selected facilities' governing bodies. The governing body can request to opt out of the study.

5.4 Inclusion/Exclusion Criteria

Inclusion Criteria

For Facility

- An established US Renal Care in-center hemodialysis facility located in a county with at least two US Renal Care facilities
- Facility governing board willingness to participate

Patient

- Treatment at US Renal Care in-center hemodialysis facility
- Age ≥ 18 years

Exclusion Criteria

Patient

- Unwillingness to share limited PHI clinical data using the electronic health record (EHR). If a patient declines offered testing he/she will still be part of the analyses as long as he/she is willing to share clinical data.
- Dementia or cognitive impairment, with inability to comprehend 'opting out' of participation

5.5 Sample Size

We performed power calculations for the primary outcome of test acceptability. Briefly, we followed formulas given by Donner and Klar (2000) for the design of cluster randomized trials comparing probabilities for two groups with an adjustment for the clustered design (Variance

Inflation Factor) by dialysis facility. Assuming a type I error of $\alpha = 0.05$, 80% power ($\beta = 0.2$), a test acceptability proportion equal to 0.4 in the static arm and 0.65 in the dynamic arm – corresponding to a 25% absolute difference, a high degree of correlation between patients within the same facility (Interclass correlation coefficient, ICC=0.5), and that we will be able to recruit ~40 patients per facility (median number of patients per facility at US Renal), we will require 2480 patients from 31 facilities per intervention arm. The assumed ICC reflects the belief that we will observe a high dependence among individuals within a cluster accepting to do the test, i.e., test acceptability is likely related, through the neighborhood composition, for individuals within the facility. With this sample size we will be able to detect a difference of at least 25% for acceptability rates in the static arm ranging from 10% to 60%.

5.6 Static Testing Frequency

In discussion with the US Renal Care medical officers regarding feasibility of integrating universal testing into routine clinical care, and given that test acceptability is our chief outcome of interest, we will offer patients dialyzing in the facilities randomized to the static arm rtPCR testing once every two weeks.

5.7 Dynamic Testing Frequency

Facilities randomized to the dynamic arm will offer dialyzing patients rtPCR testing according to an adaptive testing strategy based on current estimates of community COVID-19 transmission. We anticipate that community transmission and risk of COVID-19 will evolve over the lifetime of this trial. Wastewater SARS-CoV-2 RNA loads can be used to detect COVID-19 incidence rates as low as 1 per 100 000 persons and have been demonstrated to correlate with clinical case data during the COVID-19 pandemic (Wolfe 2021, Karthikeyan 2021, Graham 2021, Huisman 2022). We will combine disease surveillance estimates based on wastewater samples with community surveillance data from the CDC to monitor current epidemic trends at the county level and guide testing strategy assignment in real time.

Using data from the preceding week, we will establish testing frequency for each facility for a period of four weeks. Facilities with high, medium, and low evidence of community COVID-19 transmission will be assigned to once weekly, once every two weeks, and once every four weeks testing respectively. After each four-week intervention period, facilities will be assigned a new testing strategy based on the current county level of COVID-19 transmission.

The data that will inform the facility assignment to testing strategies will be:

- 1) SARS-CoV-2 RNA wastewater percentile levels
Or
- 2) Number of new cases per 100,000 persons
Or
- 3) Number of hospitalizations per 100,000 persons

High, medium and low evidence of community COVID-19 transmission will be determined by pre-defined thresholds in these indicators (Table 1). If indicators suggest different transmission levels, the highest level is selected, with facilities falling into the highest frequency of testing when any one of the indicator criteria are met.

If at any given time during the trial, 95% of facilities do not meet criteria for high frequency testing then facilities will be assigned to testing frequency strategies using trial-wide tertiles of current COVID-19 incidence.

Table 1. Thresholds for levels of community COVID-19 risk by indicator

Community Risk Level	Wastewater	Clinical indicators	
	Viral percentile level ^a	New COVID-19 cases ^b	New COVID-19 hospitalizations ^b
Low	< 20 %	<50	<10
Moderate	20–59 %	50–199	NA
High	≥ 60 %	≥200	≥10

^a SARS-CoV-2 RNA wastewater levels with respect to local historical range

^b Total number per 100 000 persons in the past 7 days

5.8 Test Characteristics

The Abbott *Alinity m* SARS-CoV-2 real time rtPCR test has FDA EUA approval for testing symptomatic and asymptomatic individuals using nasal, nasopharyngeal and oropharyngeal swabs, with a positive and negative agreement rate of 100% and level of detection 100 virus copies/mL(42). The test has been independently validated(43).

5.9 Adherence

Stanford University investigators can monitor intervention adherence in a non-obtrusive manner at each dialysis facility, both in terms of the number and frequency of rtPCR tests performed, by regularly reviewing all dialysis visits and rtPCR test data recorded in the electronic health system. Based on this information, Stanford University investigators can generate reports about performance of participating facilities. These reports will be provided to the dialysis provider organization research teams who, in turn, can communicate with clinical leadership at the

dialysis facilities. The Stanford University investigators can additionally generate reports comparing adherence rates between participating dialysis units, which can be reviewed at monthly dialysis unit quality improvement meetings.

COVID-19 surveillance testing, as well as other COVID-19 safety protocols, are part of standard practice at all dialysis units. Accordingly, members of the multi-disciplinary care teams in dialysis units are trained to pay close attention to adherence these protocols. The multi-disciplinary teams will be encouraged to review adherence to rtPCR testing protocols 1) during routine monthly multidisciplinary care rounds, 2) during routine monthly quality improvement meetings, or 3) through direct communication from the trial project managers to the dialysis unit clinical leadership. To encourage adherence at an individual patient-level at units randomized to both static and dynamic testing interventions, informational materials about the trial, the risks of COVID-19 for patients receiving dialysis, and methods to prevent COVID-19 transmission, will be provided. In addition, at dynamic intervention units, current data about county-level COVID-19 community transmission will be provided to both trial participants and clinical staff. Treating nephrologists will be encouraged to discuss the importance of rtPCR testing for SARS-CoV-2 as a method to prevent transmission with trial participants and clinical staff.

5.10 Outcomes

The primary outcome is test acceptability, i.e., the proportion of tests accepted from the total number of tests offered. Statistical analyses will account for multiple observations per patient and clustering by dialysis facility.

Secondary outcomes include time to death or hospitalization. Patients on dialysis experience the highest rates of hospitalization across all CMS at-risk beneficiaries' group(9), and among the highest death rates of patients hospitalized with COVID-19. We posit that by early identification of infected persons and by reducing transmission of SARS-CoV-2 we will reduce overall hospitalizations and death among patients receiving dialysis. Hospitalizations and deaths can be ascertained from dialysis facility records since they are mandated for tracking at monthly Quality Assessment and Performance Improvement Meetings. Thus we will use the US Renal Care electronic health record to ascertain dates, and admission and discharge diagnoses for hospitalizations. We will use the electronic health record to track dates and cause of death as applicable.

5.11 Pilot Phase

[figure not shown]
We plan a pilot phase of the study for 4 US Renal Facilities; thus in total 66 facilities are anticipated to be participating in the study. Using mixed methods including patient and personnel interviews, and review of preliminary data, the pilot will assess: 1) facility personnel preference for one of two workflows for SARS-CoV-2 testing, 2) preliminary data on test acceptability and reasons for test refusal, and 3) patient feedback on patient facing documents. In discussion with US Renal Care Chief and Associate Chief Medical Officers, the two workflows to be tested in pilot phase would be offering test to all facility patients on a designated day of week, or selecting dialysis shifts throughout a weeklong period during which to offer tests. Preliminary data on test acceptability will inform estimates for test acceptability and material requirement. Patient

feedback on patient facing documents will allow us to generate patient-friendly materials that will improve patient comprehension and engagement.

6.0 PARTICIPANT ENROLLMENT

In this cluster randomized trial, potential participants will be patients dialyzing at selected US Renal Care facilities. In considering informed consent for our study, there are three major components (**Figure 2**):

PARTICIPANT ENROLLMENT

1. A survey of RADx-UP Common Data Elements which covers topics related to COVID-19 pandemic and its effects on the health and wellbeing of underserved populations. This survey is mandated by the NIH RADx-UP consortium. Participants are requested to share identifiable information as part of this survey.
2. Offer of a SARS-CoV-2 screening test (i.e., the intervention) at a frequency dictated by facility randomization assignment
3. The sharing of limited PHI clinical electronic health record data with the study team to assess outcomes

There will be 2 research information sheets associated with the study: Research Information Sheet – Trial will cover the overall study design and all three components (Appendix A). Research Information Sheet – Survey will be specifically shared prior to the electronic RADx-UP survey (Appendix B).

Following the precedent of the pragmatic TiME trial, which was conducted under waiver of consent (see Dember et al JASN May 2019, 30 5 890-903; DOI: <https://doi.org/10.1681/ASN.2018090945>), we request waiver of consent for components 2&3. The detailed TiME trial rationale for waiving consent is attached to this IRB application. The TiME trial showcased the willingness of patients to share clinical data for the purposes of research, as >99% of enrolled patients allowed data sharing.

6.1 Rationale for Waiver of Informed Consent

6.1.1 The intervention involves no more than minimal risk

All three components of the study are considered no more than minimal risk because:

- i) the intervention consists of a SARS-CoV-2 screening test offered at varying frequency, which is being routinely administered in many settings in the United States (including in hospitals, schools, offices and airports) as well as in many other countries, without informed consent. Patients may opt out of taking the offered test at any time.
- ii) There are minimal to no safety concerns related to SARS-CoV-2 screening tests. The selected SARS-CoV-2 screening tests (the Abbott Alinity rtPCR test) has a positive and negative agreement rate of 100% and level of detection 100 virus copies/mL. Thus, we expect minimal false positive or false negative result rates.
- iii) The NIH mandated RADx-UP survey is a validated instrument currently employed across more than 100 sites with well-established and embedded processes for secure data acquisition, transfer and storage. Since this patient-facing survey does request PHI including name, address, medical record number as available, it will be accompanied by a clear research information sheet identifying the PHI data components in simple language. The research sheet will also explain to the patient how identifiable information will be stored and managed separately from anonymized data, and clearly explains in simple terms the processes for privacy protection.
- iv) Electronic health record data obtained from US Renal Care will be anonymized with a limited PHI obtained zip code of dialysis facility, dates of SARS-CoV-2 testing, dates of COVID-19 diagnosis, hospitalization, deaths, or transfers of care. This limited PHI will have low risk for traceability back to individual participants. Patients will have the opportunity to ‘opt out’ of sharing any clinical data by simply informing a designated member of their care team likely to be the dialysis nurse at any point during the study. Working with the US Renal Care clinical research coordinator, any patients deemed by dialysis facility social workers to lack capacity for ‘opt out’ consent will be eliminated from the dataset. Any patients requesting to opt out will also be eliminated from the dataset.

6.1.2 The waiver or alteration will not adversely affect the rights and welfare of the participants

All patients already dialyzing at selected facilities will receive Research Information Sheet – Trial explaining the study aims and design, including information about opting out of testing and anonymized data sharing. Patients initiating dialysis treatment at a participating facility during the time period of the study will be provided with the Research Information Sheet – Trial at the time they start dialysis. The screening tests will be offered without any mandate to the participant. Patients will be provided with an opportunity to opt out of electronic health record data sharing. No changes will be made to current dialysis facility standards of care around the COVID-19 pandemic.

6.1.3 The research could not practicably be carried out without the requested waiver or alteration

Because the randomized facility selection will be determined before patients are enrolled, a requirement for patient-level informed consent would severely compromise the generalizability and assessment of primary outcome of the trial. Patients who provide informed consent to proceed within the trial will have a much higher likelihood of test acceptance—the primary outcome—and will not be representative of the overall dialysis population. Thus, information gleaned from such a study will not be informative of the real-world effect of offering SARS-CoV-2 test-based screening in dialysis facilities.

Furthermore, to generate information valid nationally and enriched with information from the underserved populations, we plan to enroll up to 62 facilities throughout the US Renal Care Network, including those in remote areas (e.g., Alaska). We also plan a short and synchronous time period—3 months—in order to rapidly generate data relevant to the ongoing public health emergency related to the COVID-19 pandemic. We cannot practically have available study personnel for informed consent across all selected facilities, covering all potential patient interface times (typically 5 am- 9 pm, 7 days a week).

Two research information sheets—one for the overall trial, one tied to the specific electronic survey—will be distributed and will cover the typical elements of the informed consent. Requiring signed consent will make this minimal risk study infeasible.

6.1.4 For research using identifiable private information or identifiable biospecimens, the research could not practicably be carried out without using such information or biospecimens in an identifiable format

For participants who opt to take the **NIH RADx-UP Common Data Elements survey**, they will be requested to share following PHI elements:

- Name
- Date of birth
- Address, including zip code
- Email
- Medical record number
- COVID-19 dates as applicable

The RADx-UP initiative is making a concerted effort to reach underserved populations and wants to be able to ascertain identifiable information so as to allow linkage of data to other NIH, CMS and claims databases. Furthermore, another aim of gathering this identifiable information is to enable RADx-UP to reach back out to these participants as additional opportunities for interventions arise.

Additionally, Stanford University will receive **the following limited PHI elements from the electronic health record** on all patients in the participating facilities.

- Patient residence zipcode
- Dates of SARS-CoV-2 screening tests offered and resulted
- Dates of COVID-19 vaccination
- COVID-19 dates
- Dialysis facility USRC ID and zip code
- Hospitalizations, dates and admission and discharge diagnosis as applicable
- Death, dates and cause as applicable
- Transfer out of facility date as applicable

This limited PHI dataset is required to track test results, facilitate appropriate care, and enable assessment of key secondary outcomes (cases, hospitalizations, and deaths). This outcome assessment will help to generate a model for surveillance of COVID-19 and other infectious diseases among patients receiving in center dialysis.

6.1.5 Whenever appropriate, the participants or legally authorized representatives will be provided with additional pertinent information after participation

Participating facilities will be informed of the study results as soon as they become

Available, so that patients may be informed. Furthermore, a major objective of the study is to ensure feasibility, generalizability, and scalability, in close partnership with US Renal Care. We plan to identify an optimal testing frequency at dialysis facilities that will enable reduction in transmission and early identification of COVID-19. The results of this study will thus directly inform policy for SARS-CoV-2 screening in dialysis facilities nationwide.

6.2 Rationale for Waiver of HIPAA

6.2.1 The researchers require access to the PHI to conduct the research.

The RADx-UP Common Data Elements survey PHI elements are a mandated element of the grant. They will allow linkage of patient information to other databases and enable the NIH to recontact the underserved population should opportunities for additional interventions arise (e.g., among participants expressing vaccine hesitancy). Participants will receive detailed information about data protection for their identifiable health information, including that these data will be kept in a separate repository hosted only at the RADx-UP CDCC and the initial project site (Stanford University). Stanford University also requires limited PHI data from patients at the selected facilities in order to assess key secondary outcomes (detected cases, deaths, and hospitalizations) that will factor into determining the effectiveness of the intervention. We will offer patients the option to ‘opt out’ of inclusion in this limited PHI dataset, although we expect few will take this option based on the precedence of the TiME trial.

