7.5 Testing at Ascend Clinical Laboratory	20
7.6 Test Results	21
7.7 Data Collection	21
7.8 Data Confidentiality Procedures.....	22
7.8.1 RADx-UP Common Data Elements Survey	22
7.8.2 Limited PHI Electronic health record	22
7.9 Data extraction and transfer procedures	23
7.9.1 RADx-UP Survey	23
7.9.2 Limited PHI Data.....	23
7.10 Statistical Analysis Plan.....	23
8.0 DATA AND SAFETY MONITORING.....	23
9.0 EXIT SURVEY	25
10.0 REFERENCES.....	25
11.0 APPENDIX	30

PROTOCOL OVERVIEW

In this study we plan to offer SARS-CoV-2 screening tests at up to 62 selected US Renal Care dialysis in order to: reduce transmission, and detect early cases and prevent serious illness. This clinical trial is part of the NIH Rapid Acceleration of Diagnostics- Underserved Populations (NIH-RADx-UP) initiative (<https://radx-up.org/about/>), whose goal is to improve access to COVID-19 testing in underserved communities. Patients receiving dialysis have an 8-fold higher risk for hospitalization and 15-fold higher risk for death from COVID-19 compared with the general population. Patients receiving dialysis also disproportionately belong to racial/ethnic minority and economically disadvantaged groups. Thus the goals of this project are to increase availability of highly sensitive and specific testing for SARS-CoV-2 infection in a medically vulnerable and disadvantaged population.

Approach: This is a pragmatic cluster (facility-level) randomized clinical trial to test the patient level acceptability of two strategies for offering test-based screening at the dialysis facility. We will be offering anterior nares, rtPCR tests at a static frequency (arm 1) versus a dynamic frequency anchored to county COVID-19 spread (arm 2). After a pilot in four facilities, we plan to scale up the study to up to 62 dialysis facilities within US Renal Care. Ascend Clinical Laboratory will provide testing supplies, process testing, and return results to facilities. Abbott Molecular will provide supplies for the Alinity m SARS-CoV-2 rtPCR assay (approved under FDA EUA) at discounted costs. Stanford University will lead study design, data analysis, and dissemination of results.

Arm 1—Static frequency: selected facilities will offer testing once every two weeks to all patients coming to dialysis

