Arm 2—Dynamic frequency: selected facilities will offer testing to all patients coming to dialysis once a week if county COVID-19 spread is high, once every two weeks if county COVID-19 spread is low or moderate, and once a month if COVID-19 spread is minimal or eliminated.

Intervention time frame: 3 months

We will assess the following outcomes:

- 1 Patient level test acceptability (primary outcome)
- 2 Facility level Deaths
- 3 Facility level Hospitalization

The overall goal is to identify a highly acceptable universal testing strategy for patients receiving dialysis and prevent serious complications from SARS-CoV-2 by identifying cases early.

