3.0 TRIAL OBJECTIVES

3.1 To identify a highly acceptable SARS-CoV-2 testing strategy in dialysis facilities

The primary objective of this study is to offer SARS-CoV-2 testing to an underserved population. We hypothesize that the community COVID-19 case rate will be associated with test acceptability. We will test this hypothesis by offering testing either at a static (every two weeks) frequency (arm 1) or offering testing at a dynamic frequency tied to community COVID-19 rates. Among the two arms, we will assess differences in:

- 1) Primary outcome (assessed during the three-month period of the intervention): Proportion of offered tests accepted: # of times individuals respond yes / total # of times individuals are asked to perform the test during the 3-month period of the intervention

3.2 To evaluate effectiveness of the SARS-CoV-2 testing strategies in patients receiving dialysis

We will evaluate the clinical effectiveness of the two testing strategies by reporting and comparing:

Secondary outcomes (assessed up to one-month post completion of intervention):

- 2) Hospitalizations
- 3) Deaths

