7.10 Statistical Analysis Plan

We will compare the proportion of the total number of times individuals accept performing the test (# of times individuals respond yes / total # of times individuals are asked to perform the test) in the static versus dynamic testing frequency arms. We will use a log-binomial model predicting the probability of acceptability (Y) from intervention arm applying a generalized estimating equation (GEE) approach to take into account the clustering by dialysis facility and the multiple observations per patient. A similar method will be used for estimating the effect of the intervention on the outcome of death or hospitalization. Alternatively, we will use a frailty model which allows for a survival analysis of heterogeneous populations due to the clustering within facilities and multiple observations for each individual(46).

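### Do detected cases, named as a secondary outcome only in the waiver sections, need a definition and an analysis in the plan?

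*Combined protocol and SAP*

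**What the plan says.** Two sections name cases. Section 6.2.1 (HIPAA waiver) gives as a reason for data access the "key secondary outcomes (detected cases, deaths, and hospitalizations) that will factor into determining the effectiveness of the intervention". Section 6.1.4 (use of identifiable information) says the limited data set will "enable assessment of key secondary outcomes (cases, hospitalizations, and deaths" in the same parenthesis.

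Four sections do not:

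- The Overview lists acceptability as primary, then "Facility level Deaths" and facility-level hospitalization.
- Section 3.2, the effectiveness objective, lists hospitalizations and deaths under "Secondary outcomes (assessed up to one-month post completion of intervention".
- Section 5.10 says "Secondary outcomes include time to death or hospitalization".
- Section 7.10, after the model for acceptability, says "A similar method will be used for estimating the effect of the intervention on the outcome of death or hospitalization".

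Two statements of purpose are also relevant. The Overview offers screening "in order to: reduce transmission, and detect early cases and prevent serious illness". Section 6.1.5 says "We plan to identify an optimal testing frequency at dialysis facilities that will enable reduction in transmission and early identification of COVID-19".

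Static facilities test every two weeks (5.6). Dynamic facilities test every one, two or four weeks, reassigned every four weeks from county indicators (5.7).

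**The concern.** Section 6.2.1 gives detected cases a part in judging effectiveness, yet no section says whether a case is a screening positive or any COVID-19 diagnosis in the record. Nor does any section say over what period cases count, or whether more or fewer is the good result. The stated purposes pull both ways: less transmission means fewer cases, and earlier detection means more.

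The count also depends on the treatment. A facility that tests more often finds more of the same infections; 2.4 itself cites a 3-fold rise in detection under universal screening in 11 nursing homes. If cases were compared between arms and read as infections, an excess in the arm testing more often could be called better detection or more disease, and a real fall in infections could look like a rise. Section 6.1.5 says the results will inform national screening policy, so such a misreading would matter.

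**Working it through.** **1. The sections side by side**

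| Section | Purpose | Clinical outcomes named | Cases? |
|---|---|---|---|
| Overview | outcome list | deaths, hospitalization | no |
| 3.2 | effectiveness objective | hospitalizations, deaths | no |
| 5.10 | outcome definition | time to death or hospitalization | no |
| 7.10 | analysis | death or hospitalization | no |
| 6.1.4 | reason for identifiable data | cases, hospitalizations, deaths | yes |
| 6.2.1 | reason for data access | detected cases, deaths, hospitalizations | yes |

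The four sections that set outcomes and analysis agree in leaving cases out. The two that differ explain why data are needed.

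**2. The plan's own figure.** None is given for cases. The only sample-size figure (5.5) is for acceptability and reproduces: unpooled two-proportion formula, 0.40 against 0.65, two-sided 5%, 80% power, 58.7 per arm; variance inflation 1 + 39 × 0.5 = 20.5; 58.7 × 20.5 = 1203.5; 1203.5 / 40 = 30.1, so 31 facilities per arm and 62 × 40 = 2480 patients. It does not depend on cases.

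**3. How far frequency alone could move the count.** Infections are assumed equal in the two arms. Inputs: offer interval I = 7, 14 or 28 days (5.6, 5.7); acceptance a = 0.40 (static value in 5.5, used in both arms); detectable window D = 10 days (assumed); share found without screening s = 0, 0.3 or 0.6 (assumed; the top value is the complement of the 40% asymptomatic in 2.1).

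With k = floor(D/I) and f = (D − kI)/I, screening finds S = (1 − f)[1 − (1 − a)^k] + f[1 − (1 − a)^(k+1)]. Total detection is s + (1 − s)S.

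- I = 7: k = 1, f = 3/7; S = 0.571 × 0.40 + 0.429 × 0.64 = 0.503
- I = 14: k = 0, f = 10/14; S = 0.714 × 0.40 = 0.286
- I = 28: k = 0, f = 10/28; S = 0.357 × 0.40 = 0.143

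Weekly against two-weekly:

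- s = 0: 0.503 / 0.286 = 1.76
- s = 0.3: 0.652 / 0.500 = 1.30
- s = 0.6: 0.801 / 0.714 = 1.12

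A true 25% fall in infections would then show as 0.75 times these: 1.32, 0.98 or 0.84.

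Over D of 7 to 14 days, acceptance of 0.40 or 0.65 in both arms, and refusals either independent or fixed by patient, the weekly ratio is 1.00 to 2.00 and the four-weekly ratio 0.50 to 0.94.

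**4. A mix of frequencies.** Take a third of dynamic facilities at each frequency and weight by incidence at high : moderate : low counties.

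- Weights 1:1:1, s = 0: (0.503 + 0.286 + 0.143) / (3 × 0.286) = 1.09; s = 0.6: (0.801 + 0.714 + 0.657) / (3 × 0.714) = 1.01
- Weights 3:2:1: 1.30 and 1.05
- Weights 8:4:1: 1.43 and 1.07

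**5. False-positive rate if someone did test it.** Simulation: 31 + 31 facilities of 40, 5 to 20% infected, gamma facility variation with SD 0.5, log ratio of facility means, t test on 60 df, equal infections.

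- All dynamic facilities weekly: 42 to 84% significant at s = 0, 16 to 35% at s = 0.3, 7 to 11% at s = 0.6. With equal detection: about 5%.
- A third at each frequency, county levels balanced between arms: about 5 to 17% at s = 0 and about 1 to 6% at s = 0.3 to 0.6.

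The balance is plausible because 5.2 pairs facilities within counties. Letting levels fall independently in the two arms (same model, 10,000 trials per setting) gives about 5 to 23% and 5 to 9%.

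**The case for a change.** The strongest case for a change is that 6.2.1 does more than mention cases: it tells the ethics board that they bear on effectiveness. Deaths and hospitalizations do not measure transmission directly, so cases are the number a reader would turn to for the claim in 6.1.5. Section 5.10 uses an open form of words, so its list does not exclude them. Equal frequency would not remove the dependence either: with the acceptances assumed in 5.5 (0.65 and 0.40), a dynamic facility testing every two weeks would still detect 1.07 to 1.63 times as many cases. With no definition or direction, either result could be called a success afterwards.

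Much of this stands. The lists do differ, and detected cases cannot stand in for infections here. What does not follow is that the plan makes that mistake. No section specifies a comparison of cases between arms or draws transmission from them. Section 5.10 expects the benefit of reduced transmission to appear in hospitalizations and deaths. Section 6.2.1 says detected cases, which by its own words is a yield of testing, and yield is a fair thing to report for a screening trial. Cases also have another use, in the risk-factor objective of 3.3.

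The large figures need weekly testing at every dynamic facility and few infections found otherwise. Section 5.7 reassigns frequency every four weeks, and 7.5 says symptomatic testing is already in place, so s = 0 is apt only if a case means a screening positive.

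**Conclusion.** The inconsistency is real but needs no change to the plan. The objective, outcome and analysis sections agree with each other, and following them gives sound results on this point. Cases appear as an outcome only in parentheses that justify data access. An analyst who reports them would sensibly do so descriptively, as detection yield beside the numbers of tests offered and done. Section 7.7 already collects offer and result dates, test results and COVID-19 dates, so the report is possible as things stand.

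The size of any distortion, if cases were compared, runs from a ratio of about 1.01 (mixed frequencies, 60% found without screening) to 1.76 (all weekly, none found otherwise) in the central model. These figures rest on an assumed 10-day window, 40% acceptance in both arms and equal infections. The simulated error rates also assume a facility SD and an infection rate, and use a simpler test than the GEE model in 7.10. The conclusion does not depend on them: the plan contains no such test. It would change only if a between-arm comparison of cases were put forward as evidence on infections or transmission.
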